5.6 Number of Subjects

Up to 107 subjects will be registered in the clinical investigation in order to analyze the primary endpoints. No site may register more than 20% of the total subjects.

5.7 Total Expected Duration of the Clinical Investigation

The expected duration of each subject's participation is 2 years, including the scheduled visits and data collection for this clinical investigation that will occur at 1 month, 6 months, 1 year and 2 years. Subjects will be exited from the trial at the conclusion of their 2-year follow-up visit. Therefore, the total duration of the clinical investigation is expected to be consisting of approximately plus 2 years of follow-up. Subjects will be exited from the trial at the conclusion of their 2-year follow-up visits.

6.0 TREATMENT AND EVALUATION OF ENDPOINTS

6.1 Baseline Assessment

Subject preparation will occur in accordance with standard hospital policy for the care of interventional cardiovascular subjects. The baseline assessments described below must be obtained within 30 days prior to consent, unless indicated otherwise. They will be documented in the subject medical record and on the eCRF as appropriate.

The schedule of events for this trial is located in **Section 6.5.4**.

6.1.1 Subject Demographics and Medical History

Subject history will include but not be limited to the following demographics, risk factors and comorbidities: age, height, weight, body mass index (BMI), gender, hypertension, hyperlipidemia, diabetes mellitus, smoking, ischemic heart disease (history of myocardial infarction, angina pectoris, previous percutaneous or surgical coronary revascularization), congestive heart failure, renal insufficiency, liver disease, cerebrovascular disease (known carotid artery disease, history of minor or major stroke or transient ischemic attack), and chronic obstructive pulmonary disease (COPD).) All information will be obtained and recorded in eCRF.

A medication history should be documented, including:

- Anticoagulants (warfarin, unfractionated or low molecular weight heparins, etc.);

Clinical Investigation Plan

- Antithrombotic agents (acetylic salicylic acid, thienopyridines, glycoprotein IIb/IIIa inhibitors, direct thrombin inhibitors, etc.);
- Statins or other lipid lowering agents; beta-blockers; angiotensin converting enzyme inhibitors; angiotensin-II receptor antagonists;
- Insulin and oral hypoglycemic agents;

6.1.2 Pre-procedure Laboratory Assessments

The following laboratory assessment must be obtained at pre-procedure:

- Baseline 12-lead ECG
- Cardiac biomarker tests measuring creatine Kinase-MB (CK-MB) and troponin must be conducted. If a ST-Elevation MI (STEMI) or non-ST-Elevation MI (NSTEMI) is identified based on a cardiac biomarker level, the cardiac biomarker level has to return to normal limits prior to index procedure in order for the subject to be registered in the clinical investigation. If the subject has stable coronary artery disease or silent ischemia, the pre-procedure cardiac biomarker can be obtained during procedure from the arterial sheath but prior to any angioplasty, the lab results for cardiac biomarkers can be obtained at post-procedure.
- A pregnancy test must be administered to all female subjects of childbearing potential within 7 days prior to the procedure and return as negative.
- The latest LVEF status within the past 3 months prior to the index procedure (has to be documented by any method).

Other laboratory assessments (such as blood counts, chemistry panel and lipid panel, etc.) should be obtained per site's standard of care. Baseline laboratory results related to inclusion/exclusion criteria must be available and reviewed prior to the procedure for screening.

6.1.3 Pre-Procedure Preparation

Subjects should be prepared according to the healthcare facility's standard of care for cardiology subjects undergoing PCI. The ABT NG DES 48 mm stent or other XIENCE stents to be placed should be inspected, prepared, and implanted according to the most current instruction for use (IFU).

6.1.4 Peri-Procedure Medications

Loading dose of P2Y12 inhibitor medications (clopidogrel, prasugrel, ticagrelor, etc.):

- Follow the IFU of each drug for loading dose and timing. If not indicated in IFUs, then follow the site's standard of care.

Loading dose of aspirin:

- ≥ 300 mg must be administered 0* to 24 hours prior to PCI or up to 1-hour post-procedure.
- The aspirin loading dose may be omitted for those subjects on chronic aspirin therapy (≥ 7 days).

* Zero refers to administration immediately prior to balloon pre-dilatation of the first target lesion.

Clinical Investigation Plan

It is recommended that all antiplatelet medication loading doses to be given before the procedure (within 24 hours prior to procedure), at time of procedure, or post-procedure (recommended to be within 1-hour post-procedure).

6.2 Index Procedure

6.2.1 Procedures Involved in the Use of the Device Under Investigation

For appropriate use of the ABT NG DES 48, refer to the IDE IFU and the treatment strategy section (section 6.2.4) below.

6.2.2 Baseline Angiography

Baseline angiography of the target vessel will be completed as per the angiographic core laboratory guidelines. Angiography of the vessel not treated with the ABT NG DES 48 (if required), may be performed per site standard. Baseline (prior to pre-dilatation) angiogram must be sent to the core lab or the sponsor.

6.2.3 Procedure Information Should be Collected

The following data should be collected (including, but not limited to):

- Stent use attributes (e.g., size, diameter, overlapping, and number of stents)
- Lesion characteristics (ACC/AHA Classification Scheme of Coronary Lesions)
- All reportable adverse events (AEs) (refer to section 7.3.1 Adverse Event Reporting)

6.2.4 Treatment Strategy

The following treatment strategy must be followed during the index procedure:

- Any non-target lesion must be treated first with commercially available stents (≤ 38 mm) and deemed to be successful.
- Pre-dilatation of the target lesion is mandatory and deemed to be successful.
 - The pre-dilatation balloon must be shorter than the planned stent(s) length to limit pre-dilatation injury to the area to be stented (recommended 4-6 mm shorter than the planned stent).
- Select appropriate diameter of ABT NG DES 48
 - If there is considerable vessel taper it is recommended to select a stent that matches the distal RVD to avoid over expansion of the vessel.
 - Intravascular imaging is allowed per the approved ICF and per physician's discretion. If optical coherence tomography (OCT) is used for vessel size measurement, it is recommended to follow the approved IFU for guidance. Sites using OCT for vessel sizing will be asked to provide OCT images to the Sponsor. Analysis for OCT may be conducted to assess vessel sizing.

Clinical Investigation Plan

- Use 6 or above French guiding catheter for delivery and deployment of the ABT NG DES. A guide extension, a stronger back-up support guide catheter, as well as a buddy wire, may be considered. Deploy the ABT NG DES 48 per the IFU. Do not exceed the rated burst pressure (16 atm) as indicated in the IFU of the stent.
- Post-dilatation is strongly recommended with the following guidelines:
 - Should only be performed with balloon lengths that fit within the boundaries of the stent
 - The use of a high pressure, non-compliant balloon is strongly recommended.
 - If appropriate, the delivery balloon (stent balloon) may be used for post-dilatation.
 - If considerable vessel taper exists, post-dilate the proximal/distal stented segments with a balloon that matches the corresponding proximal/distal segment RVD, if appropriate.
- Bailout procedure for the side branch should only be done:
 - If new onset of chest pain or ECG changes that suggests ischemia occur, caused by the side branch occlusion during or after stenting, side branch dilatation can be done.
 - Side branch stenting should be avoided unless severe dissection is observed.
 - If kissing balloon is required, delivery balloon must not be used.

6.2.5 Final (Post-procedure) Angiography

In all subjects, the post-procedure target lesion angiography will be performed according to the angiographic core laboratory guidelines and must be captured in the same manner used for the pre-procedure images. The procedure is considered complete after final angiographic recording of the treatment area and the guide catheter has been removed from the subject.

Final angiography of vessels not treated with the ABT NG DES 48 (if required), may be performed per site standard.

Angiographic images of the treated lesions must be sent to the Angiographic Core Lab or the sponsor.

6.3 Post-procedure

6.3.1 Post-procedure ECG

A post-procedure ECG is required by this clinical investigation. If ECG changes were observed signaling a peri-procedure MI, at least two cardiac biomarker tests are mandatory following the required post-procedure cardiac biomarker collection time window, even when the first CK-MB test is less than 1x URL.

6.3.2 Post-procedure Cardiac Biomarker Tests

At post-procedure, at least one CK-MB test and at least one troponin test are mandatory for this clinical investigation:

- The first cardiac biomarker test must to be done between 6-10 hours post-procedure.

Clinical Investigation Plan

- If the first creatine kinase MB (CK-MB) test is equal or greater than 1x upper reference limits (URL) per site's standard of care (SOC), then a second cardiac biomarker test for both CK-MB and Troponin must to be done between 12-18 hours post-procedure, or prior to discharge.
- If the first CK-MB test is < 1x URL, then a second test is not required for both CK-MB and Troponin.
- Serial cardiac biomarker tests with 6-8 hours interval are strongly recommended until discharge only when CK-MB \geq 1x URL.

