- The first cardiac biomarker test must to be done between 6-10 hours post-procedure.
- If the first creatine kinase MB (CK-MB) test is equal or greater than 1x upper reference limits (URL) per site's standard of care (SOC), then a second cardiac biomarker test for both CK-MB and Troponin must to be done between 12-18 hours post-procedure, or prior to discharge.
- If the first CK-MB test is < 1x URL, then a second test is not required for both CK-MB and Troponin.
- Serial cardiac biomarker tests with 6-8 hours interval are strongly recommended until discharge only when CK-MB ≥ 1x URL.

Clinical Investigation Plan

⁷ It is recommended that the antiplatelet medication loading dose be given before the procedure (within 24 hours prior to procedure), at time of procedure, or post-procedure (recommended to be within 1-hour post-procedure).

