All deaths are considered cardiac unless an unequivocal non-cardiac cause can be established. Specifically, any unexpected death even in subjects with coexisting potentially fatal non-cardiac disease (e.g. cancer, infection) should be classified as cardiac.

Cardiac death:

Any death due to proximate cardiac cause (e.g. MI, low-output failure, fatal arrhythmia), unwitnessed death and death of unknown cause, all procedure related deaths including those related to concomitant treatment.

Vascular death:

Death due to non-coronary vascular causes such as cerebrovascular disease, pulmonary embolism, ruptured aortic aneurysm, dissecting aneurysm, or other vascular cause.

Non-cardiovascular death:

Any death not covered by the above definitions such as death caused by infection, malignancy, sepsis, pulmonary causes, accident, suicide or trauma.

MYOCARDIAL INFARCTION [MI]

1. Peri procedure MI

a. MI per SCAI definition⁴ (J Am Coll Cardiol. 2013; 62(17):1563-70):

defined as the occurrence within 48 hours after either PCI or CABG of either:

- CK-MB above 10 x URL (*determined on a single measurement), OR
- CK-MB above 5 x URL (*determined on a single measurement), PLUS
 - new pathological Q waves in at least 2 contiguous leads or new persistent non-rate related LBBB

In the absence of CK-MB measurements and a normal baseline cardiac troponin (cTn), peri-procedural MI can also be defined as a cTn (I or T) level measured within 48 hours of the PCI rises to ≥ 70 x the local laboratory URL, or ≥ 35 x URL with new pathologic Q-waves in ≥ 2 contiguous leads, or new persistent LBBB.

b. MI per ARC 2 definition⁷ (Circulation 2018; 137, 2635-2650):

For PCI and coronary artery bypass grafting (CABG), within 48 Hours:

Clinical Investigation Plan

Absolute rise in cardiac troponin (from baseline) ≥ 35 times upper reference limit, plus 1 (or more) of the following criteria:

- New significant Q waves or equivalent
- Flow-limiting angiographic complications
- New “substantial” loss of myocardium on imaging

Significant periprocedural myocardial injury:

Absolute rise in cardiac troponin (from baseline) ≥ 70 times upper reference limit.

c. MI per 4th universal definition⁸ (*Circulation* 138, e618-e651, 2018).

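### The second biomarker draw has no time limits once its pre-discharge alternative is used, so peri-procedural MI ascertainment depends on when blood is taken

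*Protocol*

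**What the plan says.** Protocol 6.3.2 sets the sampling for peri-procedural MI:

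- First sample, all subjects: "The first cardiac biomarker test must to be done between 6-10 hours post-procedure".
- First CK-MB below 1x URL: "then a second test is not required for both CK-MB and Troponin".
- First CK-MB at or above 1x URL: a second CK-MB and troponin "must to be done between 12-18 hours post-procedure, or prior to discharge".
- Further sampling: "Serial cardiac biomarker tests with 6-8 hours interval are strongly recommended until discharge only when CK-MB" is at or above 1x URL. This is advice, not a requirement.

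The second-draw rule is repeated in 6.5.4, footnote 6 ("then a second cardiac biomarker test for both CK-MB and Troponin must to be done between 12-18 hours post-procedure, or prior to discharge") and in the laboratory row of Appendix X. Section 6.3.1 adds that, if the ECG suggests a peri-procedural MI, "at least two cardiac biomarker tests are mandatory following the required post-procedure cardiac biomarker collection time window". Section 6.4 leaves discharge to standard of care.

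Appendix II gives the SCAI definition used for TV-MI in the primary endpoint. Peri-procedural MI is "defined as the occurrence within 48 hours after either PCI or CABG of either" of two criteria. The first is "CK-MB above 10 x URL (*determined on a single measurement), OR"; the second is CK-MB above 5x URL with new Q waves or new persistent LBBB. Item 2 of the same entry treats MI more than 48 h after PCI or CABG as spontaneous, at CK-MB or troponin above 1x URL with a baseline below URL. Infarcts that cannot clearly be assigned to another vessel count as target-vessel.

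**The concern.** The 12-18 h window puts a later sample after an early raised one. The alternative attached to it has no bounds: no earliest hour, no latest hour, no minimum gap after the first draw, and no condition that the subject is leaving before 12 h.

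The subjects concerned have already shown enzyme release, and the SCAI criterion turns on a single measured value. If both samples are early, a later rise past the threshold is never measured and cannot be adjudicated. TV-MI is a component of 1-year TLF, which is tested in one open-label arm against a fixed 20%, so no concurrent comparator shares the loss. Because such a draw complies, it would not appear among the out-of-window deviations of Protocol 10.6.

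**Working it through.** **1. The plan's own figure.** Protocol 8.3 and SAP 2.4 give N = 107, true TLF 10%, goal 20%, one-sided alpha 0.05, 5% attrition and about 93% power. Evaluable subjects: 107 × 0.95 = 101.65, so 101 or 102. A Kaplan-Meier simulation (exponential event and dropout times, plain Greenwood one-sided 95% upper limit below 20%, 40,000 runs) gives 92.4%, which reproduces the stated power. The simulated test is redacted, so this method is an assumption. The exact binomial gives 86.9% at 101 and 86.1% at 102, with success at 13 events or fewer.

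**2. What the sampling text permits.**

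| First draw | Second draw | Complies? | MI rule for the second draw |
|---|---|---|---|
| 10 h | 14 h | Yes | Peri-procedural: above 10x, or above 5x with ECG criteria |
| 6 h | 7 h, discharged at 8 h | Yes | Same, but any rise after 7 h is unmeasured |
| 6 h | 50 h, before discharge | Yes, read literally | Spontaneous: above 1x URL |

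The 6-8 h spacing would rule out the second row, but it is only recommended. The ECG rule in 6.3.1 refers back to the same collection window, so it does not supply a lower limit.

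**3. Who is exposed on the early side.** A subject must have a first CK-MB at or above 1x URL but short of the MI threshold, rise past the threshold later, and have no later sample that records it. A first value already above 10x URL meets the definition by itself.

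**4. How far an early value could fall short (assumption only).** The documents give no CK-MB kinetics. Take f(t) = [(t/tp)·exp(1 − t/tp)]^k, with peak time tp and k = 1 or 2, and a true peak of 12x URL:

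| tp | f(8 h), k = 1 / k = 2 | Reading at 8 h, k = 1 / k = 2 |
|---|---|---|
| 12 h | 0.93 / 0.87 | 11.2x / 10.4x |
| 16 h | 0.82 / 0.68 | 9.9x / 8.2x |
| 20 h | 0.73 / 0.53 | 8.7x / 6.4x |
| 24 h | 0.65 / 0.42 | 7.8x / 5.1x |

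The MI is still detected with a 12 h peak, and falls below 10x with peaks at 16 h or later. This shows what one missed sample could look like, not how many there are.

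**5. Effect on the test (assumed loss).** One event is 1/101 = 0.99 points of TLF. If m points are lost on net, the chance of meeting the goal at a true TLF of 20% is the binomial lower tail at 0.20 − m, with n = 101:

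| m (points) | Exact rule, ≤ 13 events | Wald-type rule, ≤ 14 events |
|---|---|---|
| 0 | 4.3% | 7.4% |
| 0.5 | 5.5% | 9.2% |
| 1 | 7.0% | 11.5% |
| 2 | 11.0% | 17.1% |

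The documents give no discharge times and no peri-procedural MI rate, so m cannot be derived from them.

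**The case against.** **Narrow exposure.** A 6-10 h sample is always required, one value can meet the definition, and repeat tests are recommended for exactly these subjects. The early scenario also needs discharge before 12 h, and the documents do not show how often that happens. This stands, and it is why the effect is probably small.

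**Natural reading.** The clause reads most easily as a fallback for subjects who leave before the 12-18 h window, not as leave to wait beyond 48 h. That is fair, but the text does not say so.

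**The error can only lower TLF.** A reader might infer this. It is plausible for early draws but not for late ones. A raised sample after 48 h can count as spontaneous MI at a CK-MB threshold one-tenth of the main peri-procedural one, and as target-vessel by default. The late-side error can therefore run towards over-counting.

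**One missed event flips the trial.** A reader might infer this from the exact test at n = 102, where 13 events give p = 0.0386 and 14 give p = 0.0675. But the exact test is a sensitivity analysis (SAP 2.13), and the primary method is redacted. Under a Wald-type rule, 14/102 has an upper limit of 0.1373 + 1.645 × 0.0341 = 0.193, so both counts pass. The planning rate implies 0.10 × 102 = 10.2 events, below the boundary. Any threshold test changes at its boundary.

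**Same schedule in the registry.** The goal comes from a historical registry (Protocol 1.0) whose biomarker schedule is not shown. If it was similar, under-detection would affect both. This cannot be settled from the documents, so bias relative to the goal is possible but not shown.

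**Conclusion.** The point holds as a gap in endpoint ascertainment. Protocol 6.3.2, 6.5.4 footnote 6 and Appendix X allow a compliant second draw before 12 h, shortly after the first, and a later rise past the SCAI threshold would then not be measured. This can lower TLF in the single arm. Read literally, they also allow a draw after 48 h, where the same procedural enzyme release faces a different threshold purely because of draw time; that error can go either way.

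What can be shown is a draw before 12 h. That such a draw precedes the CK-MB peak is a tempting step further, but it needs kinetics the documents do not give. The number of events affected cannot be derived and is probably small. On the assumed losses above, 1 net point of TLF would raise the chance of false success from 4.3% to 7.0% (exact rule, n = 101) or from 7.4% to 11.5% (Wald-type rule). The change is worth making because it is cheap and uses time limits already in the protocol, not because the trial's conclusion is shown to be at risk.

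**What to change.** Amend Protocol 6.3.2, 6.5.4 footnote 6 and the laboratory row of Appendix X in the same terms, for subjects whose first CK-MB is at or above 1x URL:

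1. Require the second CK-MB and troponin draw at 12-18 h for every subject still in hospital at 12 h.
2. Limit the pre-discharge alternative to subjects discharged before 12 h under standard of care, with the sample taken as the last step before they leave.
3. Require any late second draw within 48 h, to match the peri-procedural window in Appendix II.
4. Use actual draw times to identify subjects with a raised but sub-threshold CK-MB and no sample at 12-48 h. Treat them as not assessable for peri-procedural MI in the tipping-point analysis already planned in SAP 2.13. The case report forms and CEC charter are separate documents, so draw times may already be collected.

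Cost: amendment wording in three places and a few more recorded window deviations. No test is added, and no subject has to stay in hospital or return for the draw.

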6.3.3 Post-procedure medication

All subjects will be maintained on post-procedure antiplatelet medication per the latest American College of Cardiology/American Heart Association (ACC/AHA)/SCAI guidelines.

These medications can be halted for medical necessity if required. However, they must be resumed as soon as possible per physician's discretion.

Any changes in antiplatelet medications will be documented in the eCRF.

6.3.4 Other Chronic Concomitant Medications

Administration of concomitant medications other than any approved P2Y12 inhibitors and aspirin are not required in this protocol. Subjects may receive other medications as needed per physician's discretion.

6.4 Discharge Plan / Assessments

Discharge is defined as the subject leaving the treating or referral hospital. Discharge will be performed per standard of care.

Subjects that smoke or use tobacco products should be asked to attend at least one tobacco cessation class. Subjects that are diabetic should be counseled on blood sugar control in which the recommended HbA1c target is < 7%.

6.5 Follow-up Assessments

All subjects registered into the clinical investigation will have follow-up assessments, which include an office/hospital visit at the investigational center at the time points listed below.

6.5.1 Follow-up for All Subjects

Subjects registered in the clinical investigation will receive the following clinical follow-up:

- 1 month (30 ± 7 days): office visit/telephone contact (office visit is strongly recommended whenever possible)
- 6 months (180 ± 14 days): office visit/telephone contact (office visit is strongly recommended whenever possible)
- 12 months (365 ± 28 days): office visit (Note: a formal office visit is required at 12-month follow-up to ensure a thorough clinical evaluation. A telephone contact is an option *only* for subjects who would otherwise be lost to follow-up due to being unable to complete an office visit)
- 24 months (730 ± 28 days): office visit/telephone contact (office visit is strongly recommended whenever possible)

Clinical Investigation Plan

Clinical follow-up visits should be conducted by the investigator or trial personnel who have been trained to the protocol.

The following information will be collected at each of the time points:

- Any adverse events
- Use and compliance of protocol required antiplatelet medication
- Details of any subsequent coronary interventions (e.g., repeat PCI or CABG)

Note that information obtained through indirect contacts with a subject's healthcare provider or immediate family member will NOT be considered as a trial visit.

